The DIVA questionnaire analyses and quantifies the impact of female genital aging. It consists of 23 items grouped into 4 constructs, which include the dimensions of daily activities, emotional well-being, sexual function, and self-esteem and body image. There are two versions of the questionnaire: the full version with 23 items, which includes 4 items on sexual function that can only be evaluated in sexually active women, and a shorter version with 19 items that can be applied regardless of sexual activity. Each item is rated on a 5-point Likert scale, with the dimension value obtained by calculating the average of the corresponding items. Higher values indicate a greater adverse impact of atrophy symptoms.

---

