3. **DIVA Questionnaire (Day-to-day Impact of Vaginal Aging):** This questionnaire assesses the impact of vaginal aging on daily life. The original version was developed by Alison J. Huang (Annex 4), Director of the Department of Medicine at the University of California, San Francisco. It included 745 postmenopausal women, from 2008 to 2012, of multiethnic backgrounds with at least one complaint of genital atrophy (dryness, burning, irritation, and itching) or pain during sexual intercourse. The questionnaire is constructed with a multidimensional scale covering 4 domains: (1) daily activities, (2) emotional well-being, (3) sexual function, and (4) self-esteem and body image. The full version consists of 23 items, with a version for women without sexual activity that includes a "not applicable" option for the sexual function domain. The items are scored between 0 and 4, and the overall score is the average of the scores in each domain, with higher scores indicating a greater impact and severity of genital atrophy symptoms. The internal consistency of the original scale in English ranged from 0.47 to 0.72, with Cronbach's alpha between 0.82 and 0.93. Confirmatory factor analysis showed appropriate structural validity with a comparative fit index of 0.987 and a standardized root mean square residual (SRMR) of 0.038. A measurement property assessment of this symptom evaluation questionnaire identified it as one of the best quality and reliable tools for assessing female genital atrophy (Annex 1 and 4).
4. **EQ-5D** is a generic instrument for measuring health-related quality of life, which generates an index representing an individual's health state. Developed by the EuroQoL group since 1987 and made public in 1990, it is based on a classification system that describes health in five dimensions: mobility, self-care, usual activities, pain/discomfort, and anxiety/depression. Each dimension has three associated severity levels: no problems (level 1), some problems (level 2), and extreme problems (level 3) experienced by the individual. Another measure used is the EQ-VAS, a 20 cm vertical visual analog scale (VAS) ranging from 0 to 100, where 0 is the worst and 100 the best imaginable health. This measure of self-perceived health is

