evaluated independently for the subject's self-perception. It is available in over 130 languages in various application formats and was validated for European Portuguese in 2013 by Ferreira. It is considered reliable and valid, showing moderate to high correlations with other health status and quality of life measures for various diseases, and the purpose of using this questionnaire is to verify the concurrent validity of DIVA (Annex 5).

5. **FSFI-6 (Female Sexual Function Index)** is an instrument developed by Isidori, based on the longer version of the original questionnaire but designed for easier clinical use, as it is quick to complete but still maintains good internal consistency (Cronbach's alpha of 0.79) and excellent accuracy for differentiating clinical populations, with sensitivity and specificity above 94%. It was validated in the Portuguese population by Pechorro, including 6 items that evaluate 6 domains of sexuality: desire, satisfaction, excitement, lubrication, orgasm, and pain. This scale will be used for convergent assessment of the sexual domain of DIVA (Annex 6).

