#### **Parte B. Durante as últimas 4 semanas, com que frequência os sintomas vaginais como: secura, ardor, irritação ou comichão, fizeram com que se sentisse:**

6. Deprimida ou em baixo?

0 Nunca   1 Raramente   2 Às vezes   3 Frequentemente   4 Quase sempre

7. Embaraçada?

0 Nunca   1 Raramente   2 Às vezes   3 Frequentemente   4 Quase sempre

8. Frustrada ou ressentida?

0 Nunca  1 Raramente  2 Às vezes  3 Frequentemente  4 Quase sempre

9. Mal consigo própria?

0 Nunca  1 Raramente  2 Às vezes  3 Frequentemente  4 Quase sempre

**Parte C. As perguntas que se seguem são sobre o impacto dos seus sintomas, nas relações sexuais e outros tipos de atividade sexual, como autoestimulação ou masturbação. Durante as últimas 4 semanas, sintomas vaginais como: secura, ardor, irritação ou comichão, afetaram:**

10. O seu desejo ou interesse em ter relações sexuais ou outros tipos de atividade sexual (autoestimulação ou masturbação)?

0 Nada  1 Um pouco  2 Moderadamente  3 Bastante  4 Extremamente  
 Não aplicável- não tive atividade sexual de nenhum tipo recentemente.

11. A frequência com que teve relações sexuais, ou outros tipos de atividade sexual (incluindo autoestimulação ou masturbação)?

0 Nada  1 Um pouco  2 Moderadamente  3 Bastante  4 Extremamente  
 Não aplicável- não tive atividade sexual de nenhum tipo recentemente.

12. A sua capacidade de ficar excitada durante a atividade sexual (incluindo autoestimulação ou masturbação)?

0 Nada  1 Um pouco  2 Moderadamente  3 Bastante  4 Extremamente  
 Não aplicável- não tive atividade sexual de nenhum tipo recentemente.

13. A sua capacidade de espontaneamente se dedicar á atividade sexual (incluindo autoestimulação e masturbação)?

0 Nada  1 Um pouco  2 Moderadamente  3 Bastante  4 Extremamente  
 Não aplicável- não tive atividade sexual de nenhum tipo recentemente.

14. A sua capacidade de relaxar e desfrutar da atividade sexual (incluindo autoestimulação ou masturbação)?

0 Nada    1 Um pouco    2 Moderadamente    3 Bastante    4 Extremamente

Não aplicável- não tive atividade sexual de nenhum tipo recentemente.

15. O nível de prazer que experienciou durante a atividade sexual (incluindo autoestimulação ou masturbação)?

0 Nada    1 Um pouco    2 Moderadamente    3 Bastante    4 Extremamente

Não aplicável- não tive atividade sexual de nenhum tipo recentemente.

16. O seu desejo ou interesse em ter um relacionamento sexual?

0 Nada    1 Um pouco    2 Moderadamente    3 Bastante    4 Extremamente

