Never	Rarely	Sometimes	Fairly often	Very often

9. Bad about yourself?

 0	 1	 2	 3	 4
Never	Rarely	Sometimes	Fairly often	Very often

**PART C.** The following questions ask about the impact of your symptoms on vaginal sexual intercourse as well as other types of sexual activity such as self-stimulation or masturbation. During the past four weeks, have vaginal symptoms such as dryness, soreness, irritation, or itching affected:

10. Your desire or interest in having sexual intercourse or other types of sexual activity (including self-stimulation or masturbation)?

0      1      2      3      4  
Not at all      A little bit      Moderately      Quite a bit      Extremely

11. How frequently you had sexual intercourse or other types of sexual activity (including self-stimulation or masturbation)?

0      1      2      3      4  
Not at all      A little bit      Moderately      Quite a bit      Extremely

12. Your ability to become aroused during sexual activity (including self-stimulation or masturbation)?

0      1      2      3      4  
Not at all      A little bit      Moderately      Quite a bit      Extremely

Not applicable – I have not had sexual activity of any kind recently

13. Your ability to be spontaneous about sexual activity (including self-stimulation and masturbation)?

0      1      2      3      4  
Not at all      A little bit      Moderately      Quite a bit      Extremely

Not applicable – I have not had sexual activity of any kind recently

15. The amount of pleasure you experienced during sexual activity (including self-stimulation or masturbation)?

0      1      2      3      4  
Not at all      A little bit      Moderately      Quite a bit      Extremely

Not applicable – I have not had sexual activity of any kind recently

16. Your desire or interest in being in a sexual relationship?

0      1      2      3      4  
Not at all      A little bit      Moderately      Quite a bit      Extremely

17. Your confidence that you could sexually satisfy a partner?

0      1      2      3      4  
Not at all      A little bit      Moderately      Quite a bit      Extremely

18. Your overall satisfaction with your sex life?

0      1      2      3      4  
Not at all      A little bit      Moderately      Quite a bit      Extremely

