#### **Recommended scoring**

Total scores for each domain scale are computed by calculating the average of scores for the corresponding individual items. The possible score range for all domain scales is 0 to 4, with higher scores denoting greater impact of vaginal symptoms.

Two versions of the sexual functioning scale are available: 1) a short, 5-item version that can be administered to all postmenopausal women, regardless of sexual activity status; and 2) a longer, 9-item version that includes 4 additional items (12, 13, 14, and 15) that are only appropriate for women with a history of recent sexual activity.

Activities of daily living domain: items 1, 2, 3, 4, 5

Emotional well-being domain: items 6, 7, 8, 9

Sexual functioning domain (short version): items 10, 11, 12, 16, 17, 18

Sexual functioning domain (longer version): items 10, 11, 12, 13, 14, 15, 16, 17, 18, Self-concept and body image domain: items 19, 20, 21, 22, 23

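### The Annex 4 scoring key lists six items for a DIVA short sexual scale that the same note calls 5-item; item 12 is the surplus, and the FSFI-6 comparison carries a secondary, conditional caution

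*Protocol*

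**What the plan says.** **Scoring of the DIVA sexual domain.** Annex 4 (Recommended scoring) sets each domain score as the mean of its items, on a 0–4 scale. It offers two forms of the sexual scale. One is "a short, 5-item version that can be administered to all postmenopausal women, regardless of sexual activity status". The other has nine items, adding "4 additional items (12, 13, 14, and 15) that are only appropriate for women with a history of recent sexual activity". The item list just below reads "Sexual functioning domain (short version): items 10, 11, 12, 16, 17, 18". The Project Rationale describes a 23-item questionnaire with four items for sexually active women, and "a shorter version with 19 items that can be applied regardless of sexual activity".

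**The forms.** On the English form (Annex 4, Part C), item 12 has a not-applicable box. Items 10, 11, 16, 17 and 18 have none; item 16, for example, is "16. Your desire or interest in being in a sexual relationship", followed by the 0–4 answers only. The Portuguese form (Annex 1, Part C) prints "Não aplicável- não tive atividade sexual de nenhum tipo recentemente" under all nine items. This agrees with the Data Collection Instruments section, item 3, which speaks of a not-applicable "option for the sexual function domain".

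**The comparator.** Of FSFI-6, the Data Collection Instruments section, item 5, says "This scale will be used for convergent assessment of the sexual domain of DIVA". EQ-5D is named there for DIVA as a whole. In Annex 6, FSFI-6 items 2, 3, 4 and 6 give code 0 to a woman with no sexual activity or no attempt at intercourse, while items 1 and 5 run from 1 to 5. The Inclusion Criteria do not require sexual activity.

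**The concern.** The list in Annex 4 is the protocol's only item-level key for scoring the instrument that the study sets out to validate. Scored literally, it brings into the short scale an item that the same note holds unsuitable for women without recent activity. Short-domain reliability, structure and means could then be computed on a scale that differs from the one described.

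The secondary point concerns the one comparator named specifically for the sexual domain. Its zero codes sit below the worst functional answer. If inactive women also answer Part C of DIVA, a correlation over all women mixes symptom impact with the mere fact of inactivity.

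**Working it through.** **1. Counting items**

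Inputs, all from Annex 4: daily living, items 1–5 (5); emotional well-being, 6–9 (4); longer sexual scale, 10–18 (9); self-concept, 19–23 (5).

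- Full form: 5 + 4 + 9 + 5 = 23, as the Project Rationale states.
- Longer scale minus the four reserved items: {10,…,18} without {12, 13, 14, 15} = {10, 11, 16, 17, 18}, which is 9 − 4 = 5 items, as the prose of Annex 4 states.
- Short form with that scale: 5 + 4 + 5 + 5 = 19, as the Project Rationale states.
- Short form with the printed list {10, 11, 12, 16, 17, 18}: 5 + 4 + 6 + 5 = 20, which matches no stated figure.

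The overlap between the printed short list and the reserved items is {12}. Item 12 is also the only one of the six with a not-applicable box on the English form.

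**2. Effect on a woman's score**

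Let m be her mean on items 10, 11, 16, 17 and 18, and x her answer to item 12.

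- Shift = (5m + x)/6 − m = (x − m)/6.
- Example: m = 2, x = 4 gives (4 − 2)/6 = 0.33.
- Maximum: |x − m| = 4 gives 4/6 = 0.67.
- If item 12 is marked not applicable and only answered items are averaged, the mean is m and the shift is 0.

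**3. The FSFI-6 zeros**

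Assumption: the total is the simple sum of the six items, since Annex 6 prints no total rule.

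- Active on all items: 6 × 1 = 6 to 6 × 5 = 30.
- Fully inactive: four zeros plus items 1 and 5, so 2 to 10 whatever her vaginal symptoms.

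The effect on the correlation depends on quantities the documents do not give. As an illustration only, assume 230 women, 30% inactive, latent correlation −0.6 between impact and function, item loading 0.8 and five equally likely answers. Score DIVA as the 9-item mean in active women and the 5-item mean in inactive women, all of whom answer Part C.

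| Assumed latent correlation of inactivity with impact | Pooled r |
|---|---|
| −0.3 | −0.22 |
| 0 | −0.37 |
| 0.2 | −0.44 |
| 0.4 | −0.53 |
| 0.5 | −0.56 |

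The correlation in active women alone is −0.50 to −0.54. If all inactive women tick not applicable, the pooled and active-only values coincide. A second simulation with stronger assumed correlations and the same 30% inactive moved the inactive women's mean impact from 0.5 SD below to 1 SD above that of active women. An active-only r of −0.74 became −0.27 to −0.69, and one of −0.85 became −0.42 to −0.77. So the result can be marked attenuation, almost none, or slight inflation.

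**The case against.** **On the item list.** Annex 4's own prose and the Project Rationale expose the slip, so a careful analyst would notice it. Active women can be scored on the nine-item list, which is printed correctly. An inactive woman who ticks not applicable on item 12 may contribute no value for it. The 0.67 maximum needs item 12 at one end of the scale and all five others at the other. All of this stands and limits the consequence. It does not remove the contradiction. A reader might infer that every short-domain score will be wrong; the documents do not support that, because the shift arises only where item 12 is answered and the printed list is used.

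**On FSFI-6.** The protocol fixes no analysis set, DIVA form or total rule for this comparison, and its Statistical Analysis section leaves methods open. Who enters a validity correlation is commonly settled in an SAP, which is not at hand. The Portuguese form that participants fill in offers not applicable on all nine Part C items, so inactive women who use it throughout leave the comparison by themselves. This stands. A reader might infer that the convergent check is biased, or that it will understate validity. Neither follows: every simulation input is assumed, the direction is not fixed, and the effect can be nil.

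**On excluding inactive women.** A tempting remedy is to restrict the analysis to women with no 0 on FSFI-6 items 2, 3 and 4. But item 4 is framed around intercourse, so a woman with only non-coital activity, which Part C counts, may enter 0 and be dropped. Exclusion would also leave the short domain in inactive women without any FSFI-6 comparison.

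**Conclusion.** The scoring list in Annex 4 is wrong as printed. It has six items where the same note says five, it includes an item that the note reserves for recently active women, and it yields 20 items where the Project Rationale says 19. This rests on the protocol alone and needs no assumption. The score effect is (x − m)/6, at most 0.67 on a 0–4 scale, and only for women who answer item 12 and are scored from that list.

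The FSFI-6 point is a caution and not an established error. It requires that inactive women answer Part C, that a pooled total is used, and that the SAP does not already separate the groups. Its size and direction cannot be derived from the documents.

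**What to change.** **Item list.** In Annex 4, Recommended scoring, delete item 12 from the short-version list, leaving 10, 11, 16, 17 and 18, and use this 5-item key wherever the short domain is scored. The cost is one deleted item number.

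**FSFI-6.** If the SAP does not already provide for it, add a sentence to the Data Collection Instruments section, item 5: the correlation with the DIVA sexual domain is reported separately for sexually active and inactive women, with the n in each group and the number who marked not applicable. Define activity beforehand. Annex 3, item 16 records it for everyone but states no time window, and a rule resting on a 0 in FSFI-6 item 4 should be avoided for the reason given above. Only data already collected are needed.

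The price is precision. Take r = −0.50 (assumed), so that Fisher's z is 0.549 in absolute value with SE 1/√(n − 3):

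- All 230 women: SE 0.066, 95% CI −0.59 to −0.40.
- 161 active (30% inactive, assumed): SE 0.080, CI −0.61 to −0.37.
- The remaining 69: SE 1/√66 = 0.123, so 0.549 ± 0.241, CI −0.66 to −0.30.
- 115 in each group (50% inactive, assumed): SE 0.094, CI −0.63 to −0.35.

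The inactive group shrinks further with each woman who marks Part C not applicable. In fully inactive women only FSFI-6 items 1 and 5 can vary, so their correlation should be read as descriptive.

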#### **4. Inclusion and Exclusion Criteria:**

**Inclusion Criteria:** Women who agree to participate in the study after giving their informed consent (Annex 7) and who report at least one symptom related to genital atrophy, such as dryness, itching, burning, irritation, discomfort, or pain when urinating or during intercourse, or bleeding during intercourse, affecting the external genitalia (vulva or vagina).

**Exclusion Criteria:** Pregnancy, neoplasms under treatment, inability to speak Portuguese, or any mental or physical disability that prevents coherent responses to the questionnaire.

---

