### **Project Objectives:**

**General Objective:** To determine the reliability, consistency, and validity of the psychometric properties of the Portuguese version of the DIVA questionnaire, adapted for our culture, in peri- and postmenopausal women. This validation will provide the foundation for using this questionnaire both in research and clinical practice with Portuguese women.

**Specific Objective:** To assess the discomfort of genital atrophy symptoms in the study participants and the impact of this problem on the quality of life of peri- and postmenopausal women in the Portuguese context.

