#### **Population and Study Location:**

Participants will include women that had at least one complaint of vaginal atrophy (dryness, itching, burning, irritation, discomfort, or pain when urinating or during intercourse, or bleeding during intercourse, affecting the external genitalia: vulva or vagina).

For the normative convenience sample from the general population, participants will be users of a large urban health centre, the Personalized Health Care Unit (UCSP) of Sete Rios, Lisbon. For the clinical convenience sample, participants will be users of a general gynaecology consultation at a private hospital (Hospital Dom Manuel de Aguiar) and the gynaecology consultation at a public hospital (Hospital Santo André), both located in an urban centre in Leiria, another group of participants came from a private gynaecologic consultation of north of Portugal, at Braga city, aiming to gather 230 valid tests, following COSMIN recommendations, to allow for an assessment of invariance correlation.

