## **Data Collection Instruments:**

The methodological approach is a cross-sectional descriptive study of qualitative and quantitative data, including dependent and independent variables organized into a self-administered form completed by the participants. This form includes 5 questionnaires:

1. **Symptom Questionnaire:** This questionnaire will screen participants to be included in the study who must report at least one symptom associated with genital atrophy. The symptoms include dryness, itching, burning, irritation, discomfort or pain when urinating or during intercourse, or bleeding during intercourse, with each symptom rated on a 5-point Likert scale from 0 (no discomfort) to 4 (extreme discomfort) (Annex 2).
2. **Sociodemographic and Clinical Questionnaire:** This questionnaire will characterize the study participants. The sociodemographic section will include variables related to biological profile, such as gender and birth date, as well as socioeconomic variables like marital status, education, and professional activity. Finally, it will cover clinical variables related to gynaecological function, comorbidities, and treatments (Annex 3).

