## **8. Process Implementation:**

- Provision of "Link" at the selected data collection units the materials (questionnaires, informed consents, and envelopes).
- Distribution of data collection materials to data collection units by colleagues interested in collaborating.
- Identification of participants in the clinic, either because they express complaints or through regular medical history taken during consultation.
- Invitation to identified participants to complete the questionnaire in the nearest waiting room, in a more private space designated for the process.
- Sealing of the envelope in person in the consultation room and placing it in a closed box with a slot for insertion.
- Return of completed questionnaires to the Principal Investigator.

---

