**5. Current Occupation (or previous occupation if retired):**

- Executive/Manager
- Specialist in intellectual and scientific professions
- Technicians and intermediate-level professionals
- Administrative and similar staff
- Service personnel and salespeople

- Industrial workers, agriculture, cleaning

6. **Profession:** \_\_\_\_\_

7. **Do you smoke?**

- Yes
- No

8. **Do you drink wine weekly (more than 3 glasses)?**

- Yes
- No

9. **Type of residence:**

- Owned
- Rented
- Shared
- Apartment
- House
- Nursing home

10. **Menopausal status:**

- Perimenopausal
- Don't know
- Postmenopausal

**Age of menopause:** \_\_\_\_\_ years

11. **Ner of pregnancies:** \_\_\_\_\_ **Ner of vaginal births:** \_\_\_\_\_ **Ner of caesarean sections:** \_\_\_\_\_

12. **Gynecological surgeries:**

- No
- Yes

**If yes, which ones:** \_\_\_\_\_

13. **Hormonal treatments (creams or vaginal suppositories):**

- No
- Yes

**If yes, which one:** \_\_\_\_\_

14. **Do you use vaginal lubricants?**

- No
- Yes

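### The eligibility criteria do not restrict entry to the peri- and postmenopausal women named in the objectives, and the menopausal-status item has no premenopausal option

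*Protocol*

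**What the plan says.** The Project Objectives name the target population twice. The general objective is to establish the psychometric properties of the Portuguese DIVA, "adapted for our culture, in peri- and postmenopausal women". The specific objective concerns symptom discomfort and its impact on the "quality of life of peri- and postmenopausal women in the Portuguese context".

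The sections that decide who enters are worded differently:

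- Population and Study Location: "Participants will include women that had at least one complaint of vaginal atrophy".
- Data Collection Instruments, Symptom Questionnaire: "This questionnaire will screen participants to be included in the study who must report at least one symptom associated with genital atrophy".
- Section 4, inclusion: women who consent and "who report at least one symptom related to genital atrophy, such as dryness, itching, burning, irritation, discomfort", with urinary and intercourse-related complaints also listed. The exclusions are pregnancy, neoplasm under treatment, not speaking Portuguese, and disability that prevents coherent answers.
- Section 8: "Identification of participants in the clinic, either because they express complaints or through regular medical history taken during consultation".

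Menopausal status is asked only in Annex 3, which serves to characterise participants and not to screen them. The options of item 10 are "Perimenopausal - Don't know - Postmenopausal". Annex 3 also records age, age of menopause, contraceptive treatment and hormonal treatment for menopause. It has no question on last period or menstrual pattern.

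**The concern.** The product of this study is a claim that the questionnaire is reliable and valid in a named population, meant to support research and clinical use. That claim needs the analysed sample to be that population, and the written criteria do not ensure it. Recruitment is by convenience from a general health centre and gynaecology consultations. Several qualifying symptoms, such as itching, burning, irritation and pain on urination, are not confined to menopause. The protocol itself anticipates women of reproductive age, since it excludes pregnancy and asks about contraception.

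If premenopausal women enter, reliability, validity and symptom-impact results could be attributed to peri- and postmenopausal women when some respondents fall outside that group. Because item 10 cannot record premenopausal status, a later analysis plan cannot fully undo this: the category was never collected.

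**Working it through.** **1. Text comparison.** I looked for any age, menstrual or menopausal condition.

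| Place in protocol | Peri-/postmenopausal restriction? |
|---|---|
| General objective | Yes |
| Specific objective | Yes |
| Population and Study Location | No |
| Symptom Questionnaire (screen) | No |
| Section 4, inclusion and exclusion | No |
| Section 5, recruitment | No; refers back to the section 4 criteria |
| Section 8, identification in clinic | No |
| Section 9, data collection | No; refers back to the criteria |

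Both objectives carry the restriction. None of the sections governing entry does.

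**2. Following one case.** Take a premenopausal, non-pregnant woman with vulvar itching who consents. She meets the inclusion criteria and no exclusion applies. At item 10 she must choose perimenopausal (in target, wrongly), choose don't know, or leave it blank. Age of menopause would be empty for her, but may also be empty for a perimenopausal woman, so it does not separate the two. Age, contraceptive use and menopausal hormone treatment identify clearly young women but do not settle cases near the boundary.

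**3. The planned number.** The protocol aims for 230 valid tests, citing COSMIN recommendations. It gives no inputs from which 230 can be re-derived. The figure equals 23 items × 10, but the protocol does not state that rule, so I do not count this as a reproduction.

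**4. Scale, under assumed shares.** Let f be the share of the 230 outside the target. The protocol gives no age or menopausal distribution, so every f below is an assumption. Each 1% is 230 × 0.01 = 2.3 women.

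- In-target number: 230 × (1 − f)
- Collection needed to keep 230 in target: 230 / (1 − f), rounded up
- 95% half-width of a mean domain score, in SD units: 1.96 / √n, with n the in-target number

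| f | In-target n | Needed for 230 in target | Half-width (SD) |
|---|---|---|---|
| 0 | 230 | 230 | 1.96/√230 = 0.129 |
| 5% | 218.5, about 218 | 242.1 → 243 | 0.133 |
| 10% | 207 | 255.6 → 256 | 0.136 |
| 20% | 184 | 287.5 → 288 | 0.144 |
| 30% | 161 | 328.6 → 329 | 0.154 |

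Restricting to the target therefore costs little precision for a mean score. This speaks to the specific objective. It does not measure any bias in reliability or validity estimates, which cannot be computed from the protocol.

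**The case against.** The strongest reply is that the menopausal setting is implicit. The Project Rationale presents vulvovaginal atrophy as a component of the genitourinary syndrome of menopause, and that syndrome is a key word. A symptom related to genital atrophy could then mean one already attributed to menopause, with the recruiting clinician making that judgement. Item 10, by omitting a premenopausal option, fits a design that took a peri-/postmenopausal sample for granted. This shows likely intent, but it sets no criterion: the symptoms are self-reported, the list is open, no diagnosis of atrophy is required, and Annex 2 does not mention menopause.

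Other points stand in part:

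- The title and consent pages, including Annex 7, were not available to me, and Annex 3 is shown only in English. A restriction on those pages would still leave section 4 and the population paragraph to be reconciled.
- The original scale was developed elsewhere: "It included 745 postmenopausal women". This study adds perimenopausal women by design, so it departs from that reference even with perfect enforcement. The comparison adds little weight to the concern.
- No direction of bias is shown, and the women hardest to classify are those closest to the target. This limits the severity.
- With a stated end date of 22/01/2024, a new criterion may come too late, and the choice of analysis set commonly belongs in a SAP. Eligibility and the response options are protocol matters, however, and a SAP cannot recover an unrecorded category.
- Adding the words peri- or postmenopausal without a definition would not resolve the boundary. I accept this, and the fix asks for a definition.

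**Conclusion.** The concern holds. The protocol as written admits women outside the population named in both objectives, and its only menopausal-status item cannot identify them. I am confident of the textual mismatch and the missing option. The effect on the results is unknown: the out-of-target share is not given and may be small if recruiters applied an unwritten restriction. Under assumed shares of 5% to 30%, between about 12 and 69 of the 230 tests would be out of target (230 − 218 and 230 − 161). The problem is limited and partly recoverable. It should be fixed, because the population label is part of the study's conclusion, but it does not invalidate the design.

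**What to change.** **If data collection is open.** State in section 4 and in Population and Study Location that participants must be peri- or postmenopausal, with the operational definition the investigators intend. Add a premenopausal option to Annex 3 item 10, preferably with a short menstrual-history question. The cost is an inclusion line, a tick-box, optionally one further question, and a few women screened out.

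**If it has closed.** Restrict the main psychometric analysis to women classified as peri- or postmenopausal after checking item 10 against age and age of menopause. Fix in advance how don't know and blank answers are classified. Report a sensitivity analysis for those answers and for implausibly young respondents. Describe the validated population as the one actually analysed, and tabulate its age and menopausal status. No new data are needed. The analysed number falls somewhat below 230, and some misclassification near the pre-/perimenopause boundary will remain and should be stated as a limitation.
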